3.3.2 Visit Window

For visit based analyses, the variables will be summarized based on the scheduled days with adjusted analysis-defined visit windows. The adjusted analysis-defined windows are summarized below:

Table 1 Visit windows

Adjusted Defined Windows Visit	Scheduled Study Day	Maximum Windows
Baseline / Day 1	1	Study Day ≤ 1
Week 4	29	$2 \leq \text{Study Day} \leq 42$
Week 8	57	$43 \leq \text{Study Day} \leq 70$

Week 12	85	$71 \leq \text{Study Days} \leq 98$
Week 16	113	$99 \leq \text{Study Day} \leq 126$
Week 20	141	$127 \leq \text{Study Day} \leq 154$
Week 24	169	$155 \leq \text{Study Day} \leq 182$
Week 28	197	$183 \leq \text{Study Day} \leq 210$
Week 32	225	$211 \leq \text{Study Day} \leq 238$
Week 36	253	$239 \leq \text{Study Day} \leq 266$
Week 40	281	$267 \leq \text{Study Day} \leq 294$
Week 44	309	$295 \leq \text{Study Day} \leq 322$
Week 48	337	$323 \leq \text{Study Day} \leq 350$
Week 52	365	$351 \leq \text{Study Day} \leq 378$
Week 56	393	$379 \leq \text{Study Day} \leq 406$
Week 60	421	$407 \leq \text{Study Day}$

If there is more than one value per participant within an analysis visit window then the closest value to the scheduled visit date is summarized, or the earlier value if the values are equidistant from the nominal visit date. If two observations are equidistant from the scheduled visit on the same day, the non-missing one with the earlier collection time will be included in the analysis. Listings display all values contributing to a time point for a participant and highlight the value that contributed to the summary table where feasible.

If a visit window does not contain any observations, then the data will remain missing.

For the Baseline / Day 1 visit window, the visit label “Baseline” is used for baseline record as defined in Section 3.3.1.1. For measurements at Study Day 1 with a time of measurement after the start of IP administration, the visit label “Day 1” is used (indicating a post-baseline measurement). If the time of measurement at Study Day 1 is not available, it is assumed to be prior to the first administration of IP. If Study Day ≤ 1 and records not selected as “Baseline”, the visit label “Screening” will be used.

For summaries showing the maximum or minimum values, the maximum/minimum value recorded on treatment is used, regardless of where it falls in an interval.

Listings display all values contributing to a time point for a participant and highlight the value that contributed to the summary table where feasible.

3.3.3 Handling of Unscheduled Visits

Visits that fall outside the visit windows defined in the CSP will be classified as Unscheduled Visits. If an unscheduled visit is the closest visit to the scheduled visit study day or the earlier non-missing one when the values are equidistant from the nominal visit date (described in Section 3.3.2), they are included in the by visits summary tables. All

visits are considered for summaries of treatment emergent abnormalities, minimum/maximum on treatment values etc. and will be presented in the listings.

3.3.4 Multiplicity/Multiple Comparisons

The primary analysis for the primary endpoint is performed using Bayesian dynamic borrowing approach with supportive analysis performed using frequentist hypothesis testing approach. Multiplicity adjustments are not performed when testing the primary and key secondary endpoints. Nominal p-values are presented for the primary and key secondary endpoints.

3.3.5 Handling of Protocol Deviations in Study Analysis

All protocol deviations identified during monitoring of the study are recorded in the clinical trial management system (CTMS). Important protocol deviations (IPDs) are a subset of protocol deviations that may significantly impact the completeness, accuracy, and/or reliability of the study data or that may significantly affect a subject's rights, safety, or well-being.

Protocol deviations are classified as important or not important by different methods, either programmatically or manually identified, as defined in the Protocol Deviation Plan based on periodic reviews of CTMS deviation reports and Dry Runs. The Sponsor reviews the classification and provides the final determination. The list of IPDs is finalized and documented prior to CDL and unblinding. Only IPDs are listed and tabulated in the CSR.

A detailed description on how IPDs are collected and identified is referenced in the Protocol Deviation plan.

The following general categories are considered IPDs and are listed and discussed in the CSR as appropriate for the study:

- Deviation 1: Inclusion Criteria Deviations
- Deviation 2: Exclusion Criteria Deviations
- Deviation 3: Discontinuation Criteria for study product met but subjects not withdrawn from study treatment
- Deviation 4: Discontinuation Criteria for overall study withdrawal met but patient not withdrawn from study
- Deviation 5: IP Deviation

- Deviation 6: Excluded Medications Taken
- Deviation 7: Deviations related to study procedure
- Deviation 8: Other Important Deviations

3.3.6 Identifying Cases of Restricted Medication Use

Restricted medications are concomitant medications that have restrictions applied to their use. Restricted medications that are used outside of what is permitted, that are deemed to affect endpoints of interest, are considered intercurrent events.

These cases are confirmed by the medication review team who reviews potential restricted medication use (RM) cases that have been identified via programmatic rules. See the restricted medication review charter for details on the review process. See Appendix 7.4 for the programmatic rules.

Note that prohibited medications are considered a subset of restricted medications that are not permitted during the study and result in immediate premature end of treatment if taken during the study treatment period.

3.3.7 Identifying Cases of PEOT due to Lack of Therapeutic Response

The reason for early IP discontinuation is classified as “Lack of therapeutic response related” if persistent or increased disease activity at time of study intervention discontinuation compared with baseline activity was evident upon review of specific endpoints. Lack of therapeutic response related reasons include discontinuation reasons of “Condition under investigation worsened” and “Condition under investigation not improved”, and reasons that require blinded review to determine the relationship with lack of therapeutic response. These reasons are “Subject decision”, “Adverse event”, “Development of study specific discontinuation criteria”, and “Other”.

The manual review is conducted blindly by a sponsor-led Central Review Team prior to the primary CDL. PEOT charter details the data review process and documentation processes.

3.3.8 Identifying Cases of PEOT due to COVID Lockdown

The reason for early IP discontinuation is classified as “COVID lockdown” if the reason for discontinuation is related to COVID lockdown. This is identified if main reason for investigational product discontinuation = ‘Other’ with ‘COVID’COVID specified in the text on the eCRF form DOSDISC.

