### 3.9.1 IMP discontinuation in relation to COVID-19

- Participants who develop confirmed or suspected severe COVID-19 infection requiring hospitalization, ICU care or assisted ventilation must have their IMP permanently discontinued.
- Participants with laboratory (central or local) confirmed non-severe COVID-19 infection must have their IMP temporary withheld with no further IMP dosing until complete resolution of symptoms for at least 2 weeks and without any sequelae. Restart of IMP must be discussed with AZ study physician or designee.
- Participants with suspected symptomatic COVID-19 or known exposure to COVID-19 (close contact) infection i.e., no antigen or PCR test result available, must have their IMP temporary withheld and should undergo antigen or RT-PCR test (central or local lab) with no further IMP dosing until complete resolution of symptoms for at least 2 weeks and without any sequelae, or remain asymptomatic for at least 2 weeks. Restart of IMP must be discussed with AZ study physician or designee.

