4.1.1.2 Presentation

Disposition is summarized based on the all-participant analysis set and includes the following information:

- the number of participants screened for the eligibility criteria
- the number of participants who are randomized
- the number of participants who are randomized and who received at least one dose of study drug
- the number and percentage of participants who completed treatment/discontinued treatment (including reasons for IP discontinuation)
- the number and percentage of participants who completed or discontinued study (including reasons for study discontinuation)

A randomization listing is presented and includes the following information: randomization number, full enrolment number, date of randomization and randomized treatment group.

The impact of COVID-19 (i.e., participants discontinued/withdraw from study, protocol deviations) is collected in the electronic case report form (eCRF) as a variable related to global/country situation.

Tables on disposition due to global/country situation, global/country situation study disruptions (i.e., subjects with at least one disruption due to global/country situation) are provided.

A summary of number and percentage of participants in each region, each country/area and each site by treatment group and overall are provided for the FAS. Additionally, the stratification factors at randomization (as calculated from the data for SLEDAI-2K score at screening and Randomization [Day 1] OCS dose and region (mainland China versus not mainland China)) are presented with count and percentage of the participants by treatment group and overall, for the FAS.

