4.2.1.7 Supplementary Analyses of the Primary Endpoint

4.2.1.7.1 Supplementary Analysis of the Primary Endpoint – targeting the impact of PEOT due to different reasons

A supplementary analysis for BICLA response is to assess the impact of PEOT due to different reasons by combining composite, treatment policy and hypothetical strategies to handle PEOT due to different reasons. That is, intercurrent events of PEOT due to lack of therapeutic response (after blinded review of the discontinuation reasons, see Section 3.3.7 for details) will result in a non-responder (NR) status per composite strategy. PEOT due to COVID lockdown will be handled per hypothetical strategy. PEOT not due to lack of therapeutic response or COVID lockdown will be ignored per treatment policy. RM and death will still be handled using composite strategy and will be imputed as non-responders from the time such ICEs occur up to week 52. More details on the derivation rules are specified as below.

For subjects with intercurrent events of RM, death and PEOT due to lack of therapeutic response, they will be imputed as non-responders from the time such ICEs occur up to Week 52. For subjects with PEOT due to COVID lockdown, data after PEOT will not be used and will be imputed. Intermediate and terminal missing values for BILAG-2004, SLEDAI-2K and PGA will be imputed separately for each BICLA component using multiple imputation under the assumption of missing at random. Missing values of BICLA

are imputed based on the imputed values of the BILAG-2004, PGA and SLEDAI-2K components.

For each outcome and visit, 100 imputations are generated by randomized treatment group. The procedure is initiated with a seed of 12345. For analysis, each imputed dataset is analyzed separately using the CMH approach described in Section 4.2.1.5, and the single estimates is combined using PROC MIANALYZE. Each component is imputed as follows:

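### SAP 3.3.8 finds COVID-lockdown discontinuations by one reason code and one word, so infection stops coded Other can be flagged and other lockdown stops missed

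*SAP*

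**What the plan says.** SAP 3.3.8 gives a definition and then a rule. By the definition, a stop belongs to the COVID-lockdown category "if the reason for discontinuation is related to COVID lockdown". The rule reads "This is identified if main reason for investigational product discontinuation" equals *Other*, with COVID "specified in the text on the eCRF form DOSDISC". (The word COVID is printed twice at that point, which I take as a typing slip.)

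SAP 3.3.7 deals with the neighbouring category, stops due to lack of therapeutic response. It lists reason codes that need blinded review: "These reasons are “Subject decision”, “Adverse event”, “Development of study specific discontinuation criteria”, and “Other". It adds: "The manual review is conducted blindly by a sponsor-led Central Review Team prior to the primary CDL". That review is described for lack of response only.

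SAP 4.2.1.7.1 uses both categories in one supplementary BICLA analysis:
- Stops for lack of response are non-responders.
- For lockdown, "PEOT due to COVID lockdown will be handled per hypothetical strategy": data after the stop are set aside and imputed under missing at random.
- All other stops are ignored under treatment policy.

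SAP 4.2.2.5 repeats the method for SRI(4).

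Two other places bear on the point. SAP 4.1.1.2 says that the impact of COVID-19 on discontinuation or withdrawal from the study, and on protocol deviations, "is collected in the electronic case report form (eCRF) as a variable related to global/country situation". Protocol 3.9.1 says that participants with severe COVID-19 infection "must have their IMP permanently discontinued".

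**The concern.** The rule does not implement its own definition. Nothing in it requires lockdown, closure or travel restriction to be mentioned, and nothing excludes the participant's own infection. It searches one reason code, although Protocol 3.9 places inability to attend visits and unacceptable logistics under participant decision, where a lockdown stop could well be recorded. The restricted-medication rule (SAP 3.3.6) and the lack-of-response rule (3.3.7) both end in review by a team. This one does not.

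The flag determines which intercurrent-event strategy a participant receives, so an error changes the data analysed. Participants who stop treatment are asked to keep attending scheduled visits (Protocol 3.9.3, 4.3.1), so real outcomes may exist after the stop. A false flag discards them. An overlooked lockdown stop coded *Subject decision* or *Other* still goes to the lack-of-response review, where disease activity that has persisted or risen since baseline leads to non-response. The SAP does not say which category prevails when a stop meets both 3.3.7 and 3.3.8.

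**Working it through.** The plan states no figure for this category, so there is nothing to reproduce. The check has three parts.

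**1. The rule applied to invented entries.** A stop is flagged if and only if the main reason is *Other* and the text contains COVID.

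| Main reason | Text | Truly lockdown? | Flagged? | Result |
|---|---|---|---|---|
| Other | site closed, COVID lockdown | yes | yes | correct |
| Other | COVID infection, participant worried | no | yes | false flag |
| Adverse event | severe COVID-19 pneumonia | no | no | correct |
| Study-specific criteria | severe COVID-19, in hospital | no | no | correct |
| Subject decision | could not attend, COVID lockdown | yes | no | missed |
| Other | city lockdown or quarantine, site closed | yes | no | missed |
| Other | SARS-CoV-2 infection | no | no | correct |

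These entries show which errors are possible. They say nothing about how often they occur.

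**2. What each error does under SAP 4.2.1.7.1.**
- False flag: treatment policy would have used the observed data after the stop. Instead they are dropped and imputed under missing at random.
- Missed lockdown stop, not assessed as lack of response: data after the stop are used under treatment policy, not set aside as the hypothetical strategy intends.
- Missed lockdown stop with persistent disease activity: it can be assessed as lack of response under 3.3.7 and set to non-response.

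**3. Illustration of size per participant.** Assumed inputs: about 130 per arm, and an imputed response probability p equal to the pooled historical BICLA rate, 0.475 (anifrolumab) or 0.308 (placebo), both from Protocol 8.2. The actual imputation models each BICLA component separately within treatment group, so its p may differ.

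Non-response in place of imputation lowers an arm's rate by k × p / 130 for k participants:

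| k (assumed) | Anifrolumab, k × 0.475/130 | Placebo, k × 0.308/130 |
|---|---|---|
| 1 | 0.37 points | 0.24 points |
| 3 | 1.10 points | 0.71 points |
| 5 | 1.83 points | 1.18 points |
| 10 | 3.65 points | 2.37 points |

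For a false flag, replacing one observed non-response by an imputed value raises the rate by p/130, as in the first row. Replacing one observed response lowers it by (1 − p)/130: 0.525/130 = 0.40 points for anifrolumab and 0.692/130 = 0.53 points for placebo.

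The documents give no value of k, so these figures are not an estimate of the effect in this trial.

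**The case against.** The strongest reply is that the rule may work better in practice than on paper. The SAP amendment history says that 3.3.7 and 3.3.8 were added to match how the data are collected. Sites may therefore have been told to record lockdown stops as *Other* with COVID in the text. The form, its completion guidance and the discontinuation review charter are not among the documents, so this remains possible. It does not remove the mismatch between definition and rule in the SAP itself.

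Several stronger readings are tempting, and the documents do not support them:

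- *A reader might infer that infection-related stops in general are counted as lockdown.* They are not. *Adverse event* and study-specific discontinuation criteria are separate codes and are not searched. A stop for severe COVID-19 under Protocol 3.9.1 would naturally carry one of them, and non-severe infection leads to temporary withholding. Only infection stops coded *Other* with COVID in the text are exposed.
- *A reader might infer that a missed lockdown stop with missing data becomes a treatment failure.* SAP 4.2.1.7.1 does not establish this. Its sentence on imputing intermediate and terminal missing components is not clearly limited to lockdown cases, so missing data after an unflagged stop may also be multiply imputed. The firmer route to non-response is the lack-of-response review.
- *A reader might infer that the COVID analysis promised in Protocol 8.5 fails to estimate its target.* That target is COVID-19-related non-compliance, which is broader than lockdown. A match on the word COVID could even lie closer to it in some cases.
- *A reader might infer that the eCRF global/country-situation variable already solves the problem.* SAP 4.1.1.2 describes it for discontinuation or withdrawal from the study and for deviations. It does not say that the variable records the cause of stopping treatment only.

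**Conclusion.** The point holds as a mismatch between a stated definition and its stated rule, and no other section repairs it. Infection stops coded *Other* can be counted as lockdown. Lockdown stops under another code, or without the word COVID, are missed.

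The scope is narrow. Only the supplementary BICLA and SRI(4) analyses by discontinuation reason use the flag. The primary Bayesian analysis and the supportive CMH analysis treat every premature stop as non-response from the time it occurs, whatever the reason. The other supplementary BICLA analyses, on discontinuation and restricted medication, and the tipping-point analysis do not use the flag either. The primary result and the main key secondary analyses cannot change.

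The size cannot be stated. It depends on how many stops are misclassified, on how sites completed the form, and on whether data exist after the stop. The documents give none of these. The expected share of about 80% of participants from mainland China (SAP 4.7) does not supply a count of lockdown stops. The correction is still worth making before unblinding, because it is cheap and the affected analysis exists to separate stops by reason.

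**What to change.** Change SAP 3.3.8 and the discontinuation review charter as follows:

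1. Use the text match in 3.3.8 as a screen only, not as the classification.
2. Have the blinded Central Review Team of 3.3.7 assign lockdown yes or no to every premature stop, across all reason codes, before the primary database lock. It should use the free text and, where it proves to cover discontinuation of treatment, the eCRF global/country-situation variable.
3. State that the participant's own COVID infection is separate from restrictions on access to the site or to treatment, and that only the latter count as lockdown.
4. State which category takes precedence when a stop meets both 3.3.7 and 3.3.8.

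The cost is one extra yes-or-no assessment in a blinded review already planned, plus SAP and charter wording. It needs no new data collection, since the team can work from the free text if the global/country-situation variable turns out not to cover treatment stops.

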3.3.9 Data excluded from analysis

During the study, an error was identified in the electronic patient-reported outcome (ePRO) software for the simplified Chinese and traditional Chinese versions, impacting sites in mainland China and Taiwan (See more details in QE-273452 and QE-386615). This error affects the last question of the EQ-5D-5L questionnaire in ePRO software version 06.01 and earlier. The correct instruction above the visual analogue scale indicates “100 represents the best health you can imagine” and the instruction below indicates “0 represents the worst health you can imagine”. In the erroneous translated screen patients are seeing, the instruction texts upside down with the above instruction saying 100 for worst and the below instruction saying 0 for best. This discrepancy makes it extremely difficult to retrospectively verify each patient's response for each visit and ensure accuracy. After consulting with a PRO expert, the study team has decided to only use correct data for the EQ-5D-5L analysis, which will be treated as exploratory.

On 18-Dec-2024, the decision was made to exclude data collected from affected sites (sites in China mainland and Taiwan) before the software was updated to version 7.0 from the EQ-5D-5L analysis.

Therefore, the EQ-5D-5L analysis only included all data from unaffected sites (sites not in China mainland and Taiwan) and data collected from affected sites (sites in China mainland and Taiwan) after the software was updated to version 7.0.

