4.2.17.4 Not applicable. Primary Analysis of Exploratory Endpoint – EQ-5D-5L

The 5 dimensions of EQ-5D-5L (mobility, self-care, usual activities, pain/discomfort, and anxiety/depression) are summarized by timepoint as number and percentage of participants with the different health states.

Observed values and changes from baseline in VAS Score and single summary utility index, respectively, are presented longitudinally with descriptive statistics.

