4.7 China Subpopulation Analyses

Approximately 80% of the participants are estimated to be recruited from mainland China. The efficacy and safety in China subpopulation (defined as all participants from sites in mainland China) were analyzed to facilitate a benefit-risk assessment for regulatory submission in China.

Efficacy are summarised for the China subpopulation, which consists of all randomized participants from sites in mainland China in the Full Analysis Set as defined in Section 3.2.2. Selected key analyses will be conducted and stratified analyses will not include the stratification factor region for the China subpopulation. These analyses are considered descriptive/supportive only, therefore no significance testing will be performed.

Safety and tolerability are summarised for the China subpopulation, which consists of all dosed participants from sites in mainland China in the Safety Analysis Set as defined in Section 3.2.3.

The PK data is summarised for the China subpopulation, which consists of all dosed participants from sites in mainland China in the Pharmacokinetic Analysis Set as defined in Section 3.2.4.

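### SAP 3.3.9 confines the EQ-5D-5L screen error to the VAS question but, as worded, excludes the dimensions and utility index as well

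*SAP*

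**What the plan says.** SAP 3.3.9 (Data excluded from analysis) describes the fault at item level: "This error affects the last question of the EQ-5D-5L questionnaire in ePRO software version 06.01 and earlier". Participants using the simplified or traditional Chinese screens, at sites in mainland China and Taiwan, saw "the instruction texts upside down with the above instruction saying 100 for worst and the below instruction saying 0 for best". After consulting a PRO expert, "the study team has decided to only use correct data for the EQ-5D-5L analysis, which will be treated as exploratory".

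The rule that follows is set by site and software version. On 18 December 2024 "the decision was made to exclude data collected from affected sites (sites in China mainland and Taiwan) before the software was updated", and the sentence ends by naming what the data are excluded from: "before the software was updated to version 7.0 from the EQ-5D-5L analysis". The closing paragraph repeats the scope. The analysis holds everything from unaffected sites, plus data collected at affected sites after the update. Neither paragraph mentions the VAS.

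SAP 4.2.17 defines the EQ-5D-5L analysis. The five dimensions are tabulated by health state at each timepoint. In addition, "Observed values and changes from baseline in VAS Score and single summary utility index, respectively, are presented longitudinally with descriptive statistics". Section 4.2.17.1 derives the index from the descriptive system through a crosswalk to the UK value set.

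On recruitment, SAP 4.7 states: "Approximately 80% of the participants are estimated to be recruited from mainland China".

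**The concern.** The fault lies in one question, while the exclusion covers the whole instrument. A programmer who follows 3.3.9 as written would remove dimension responses and index values that the SAP gives no reason to doubt. This also conflicts with the section's own principle of keeping data that are correct.

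Three things are at stake, all within an exploratory endpoint:

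- **Precision** of the dimension and index summaries.
- **Representativeness**, because the exclusion falls on the region expected to supply most participants.
- **Change from baseline**, because a participant who loses the Week 0 record loses the index change at every later visit, even when the later visits are valid.

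**Working it through.** The SAP states no figure for the amount of data lost, so there is none to reproduce. The check is a comparison of texts, followed by simple arithmetic on the possible size.

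**1. Scope of the error against scope of the rule**

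| Element | Touched by the screen error? | Excluded by 3.3.9 as worded? |
|---|---|---|
| VAS (last question) | Yes (3.3.9) | Yes |
| Five dimensions | Not according to 3.3.9 | Yes |
| Utility index | No; calculated from the dimensions (4.2.17.1) | Yes |

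Protocol 5.3.1 supports the separation. Each dimension has its own five response options, and the VAS is a further question. The reason given in 3.3.9 is that individual responses cannot be verified afterwards when the anchors were reversed. That reason applies to the VAS alone.

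**2. Loss of baseline**

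Protocol Table 4 schedules the EQ-5D-5L at Week 0 and later visits. Protocol Table 3 (screening) does not list it. SAP 3.3.1.1 takes the last value before first dose as baseline and falls back on an earlier pre-dose value if the Day 1 value is missing or invalid. No earlier EQ-5D-5L value is scheduled. If the Week 0 record is excluded, no scheduled baseline remains, and the change-from-baseline summaries in 4.2.17.4 lose that participant throughout.

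**3. Possible size**

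Inputs: about 260 randomised 1:1 (SAP 3.2); about 80% expected from mainland China (SAP 4.7). The Taiwan share and the date of the version 7.0 update are not given.

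- Expected at mainland China sites: 0.80 × 260 = 208.
- Remaining participants, including any in Taiwan: 260 − 208 = 52, or 52/260 = 20%.

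Let f be the fraction of the 208 who lose their EQ-5D-5L data at a given visit. The retained number is 260 − 208f. With equal variance and balanced arms, the standard error of a between-arm difference is multiplied by √(260 / (260 − 208f)).

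| f (assumed) | Retained | Standard error factor |
|---|---|---|
| 0 | 260 | √(260/260) = 1.00 |
| 0.5 | 156 | √(260/156) = 1.29 |
| 1 | 52 | √(260/52) = 2.24 |

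Any Taiwan participants who lose data push the last row somewhat higher. The documents do not allow f to be narrowed.

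**The case against.** The strongest reply is that the sponsor meant only the VAS. The section says correct data will be used, and the SAP amendment history (25 March 2025) explains the addition of 3.3.9 as making clear that only error-free data enter the analysis. On the SAP's own account the dimension responses were not in error, so that principle would keep them. It is also true that the SAP nowhere says in so many words that the dimensions or index are dropped; this follows from the wording of the last two paragraphs of 3.3.9. The reply supports the narrower exclusion as the right rule, but it does not change what those paragraphs instruct. Under either intention the text needs an edit.

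A second reply is that the quality-event reports cited in 3.3.9, the waiver form cited in the amendment history, or the PRO expert's advice may justify a wider exclusion. Those records are not available here, so this stays open. The SAP itself gives no such reason.

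A third reply concerns consequence, and it largely stands. The EQ-5D-5L is exploratory. Section 4.2.17.4 specifies descriptive statistics only, although SAP Table 2 also lists a repeated measures comparison for it, and the standard error factor bears mainly on that comparison. Section 3.3.9 excludes no Lupus QoL or WPAI data.

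A reader might infer that the two arms are biased against each other. The documents do not show this. The rule depends on site and software version, not on arm or outcome; randomisation is stratified by mainland China versus not; and Protocol 8.1 keeps analysis staff blinded until database lock.

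**Conclusion.** The mismatch is real. As worded, 3.3.9 removes dimension and index data that the SAP gives no ground to distrust, and it removes the baseline for index change in participants whose Week 0 record predates version 7.0.

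The size cannot be fixed from the documents. It runs from near zero, if the update came before most visits, to about 80% or more of participants, with a standard error factor from 1.0 to about 2.2. The upper end assumes that all mainland China data precede the update, the arms are balanced and variance is equal.

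A reader might go further and conclude that most of the trial's health-status data are lost, that at least 208 participants are affected, or that what remains is dominated by other countries and late visits. None of these is supported. The 80% is an approximate recruitment estimate, not a floor. Participants enrolled at these sites after the update are not affected. Post-update data are kept, and the other patient-reported outcomes remain.

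Primary and key secondary conclusions do not depend on this. The point is worth correcting because the change is small and the data already exist.

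**What to change.** Reword 3.3.9 so that the exclusion applies to the VAS item at mainland China and Taiwan sites before version 7.0. State that the five dimensions and the utility index are kept from all sites and visits. Add a footnote on the exclusion to the VAS tables.

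This does not recover everything: VAS change from baseline stays unavailable where the baseline predates version 7.0.

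If the quality-event records show that the dimension items were also compromised, keep the wider exclusion and give that reason in 3.3.9.

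The cost is one SAP paragraph and an item-level flag in the analysis data. No new data are needed.
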